1.3 Rationale

In recent years, there has been an explosion of interest and development of technological solutions to either supplement existing mental health treatments or expand access to quality mental health services. This development was matched by patient demand with about 70% showing interest in using mobile applications (apps) to self-monitor and self-manage their mental health [1]. Internet interventions for anxiety and depression have significant empirical support [2] with outcomes comparable to therapist-delivered cognitive behavioral therapy (CBT) [3-4]. Yet, despite demonstrated efficacy, they are characterized by relatively poor adoption and adherence. One review found a median minimal completion rate (usually defined as completion of ~4 sessions) of 56% [5].

Another problem is that almost all of the research on mobile apps was conducted on apps that are not commercially available. For example, one systematic review of 5,464 abstracts identified just 5 apps that had supporting evidence from randomized controlled trials, and none of them were available commercially [6]. In contrast, apps that were commercially available typically lack evidence and/or a commitment to demonstrate outcomes.

Conversational agents, or chatbots, are software programs that use natural language as inputs and outputs instead of, for instance, menu commands (e.g., File/Save As...) or graphical inputs (e.g., clicking on an icon to open an app). Recent advancements in voice recognition have given rise to the emergence of many conversational agents such as Apple's Siri or Amazon's Alexa. Interacting in this way appears to be a more natural medium through which individuals engage with technology. People respond and converse with nonhuman agents in ways that mirror emotional and social discourse dynamics when discussing behavioral health [7].

Moreover, evidence-based in-person therapies such as CBT, traditionally assign clients opportunities to practice therapy skills outside of sessions, commonly referred to as therapy homework. Historically, it's often proven difficult to engage CBT clients in their homework on a regular basis. Conversational interfaces redefine the entire concept of therapy homework; their ability to be available in the actual moment of need, regardless of time of day or day of week, allows clients to engage with their therapy skills in-vivo, when it matters most.

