Exploratory Aim: To observe and describe the utilization and outcomes of the safety procedures utilized within this study (Safety Net Protocol, AE/SAEs and device relatedness). To describe the sample population with respect to healthcare utilization, social determinants of health, and comorbidity data for pre-study and during-study (treatment and follow-up) periods and examine associations between these factors and study clinical, alliance, engagement and satisfaction outcomes.

3. Study Population

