3.3.1 Violation of Study Plan

Participants that do not complete registration for the W-GenZD application or who do not attend a teletherapy group within the first week following randomization will not be removed from the study for failure to access the study intervention. Participants will remain in the study and will continue to receive invitations to complete survey assessments. Depending on randomized condition, those in the CBT-Lite group may attend the remaining sessions (2-4) and those in the W-GenZD group may download the app and program the duration of the 4-week intervention period. All participants randomized to this protocol, regardless of participation or withdrawal status, will be included in the intent-to-treat analysis (see section 9.0).

4. Study Design

This study will be a randomized controlled trial of W-GenZD versus CBT-lite teletherapy groups. The trial will consist of 3 primary phases: Screening/Baseline, Treatment, and a Follow-up period.

All adolescents referred to the CHKD Mental Health Program are provided an orientation about the clinical care program and participate in a brief clinical triage assessment to assess needed level of care. In general, information about the study and consent to contact is included in the welcome packet. As part of recruitment efforts, CHKD may provide families with tokens of engagement (e.g., stress balls). Based on the brief clinical triage assessment, if the adolescent is appropriate for the low-intensity intervention track, study staff will re-introduce the study during the telephone interview and assess the family's (adolescent and parent/guardian) interest in participating. Research staff will follow up with those who expressed interest, present the study, obtain informed consent and assent, facilitate assessment completion, and assess inclusion/exclusion criteria.

Adolescents who do not meet eligibility criteria will be thanked for their interest and willingness to volunteer, and will return to the routine clinical care pathway at CHKD.

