8.2 Benefits

When evaluating the risks and benefits of the proposed study, it is believed that risks are relatively minimal when compared to the potential therapeutic benefits that subjects are likely to receive. The possible benefits of receiving Woebot or participating in the CBT-lite teletherapy groups include potentially improving mood (anxiety, stress, and/or depression), acquiring practical psychotherapeutic skills (from cognitive behavioral therapy, dialectical behavior therapy, and mindfulness), and receiving psychoeducation about mental health.

Participants who improve mood may derive additional benefits should said mood improvements be associated with other psychological improvements such as interpersonal or occupational functioning. Study of the effectiveness of the W-GenZD intervention will also benefit society more generally by providing data on the efficacy of Woebot.

9. Statistical Analysis

This study was designed to assess the feasibility of delivering W-GenZD as an option for adolescents ages 13-17 years triaged into a low intensity track for mental healthcare while on a waiting list for definitive treatment.

Primary Aim: What is the feasibility and acceptability of the W-GenZD among a group of adolescents and who have been screened and triaged into low-intensity treatment within CHKD?

Hypothesis: W-GenZD will be acceptable and feasible.

Primary Endpoints: Feasibility and acceptability metrics including:

- Study enrollment rates
- URPI -Feasibility; UPRI Acceptability {12 items}
- Client Satisfaction Questionnaire (CSQ-8) {8 items}
- App engagement metrics {Woebot condition}
 - *Measure*: App engagement, including number of messages sent to Woebot by week and number of days active in the app by week
 - *Measure:* Content and program satisfaction ratings, including data collected in app (e.g., module ratings)

Analysis Plan:

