Statistical analysis will be descriptive. Continuous variables will be summarized using tables of descriptive statistics: number of participants with recorded observations, mean, standard deviation, median, first quartile, third quartile, minimum, maximum and interquartile range (IQR). Study enrollment rates will be reported. For subjects in the Woebot condition the app engagement measures will be summarized. Similarly, the content and program satisfaction ratings, including data collected in the app will be summarized. Categorical and ordinal variables will be described using frequencies and percentages. The amount of missing data will be summarized by treatment condition.

Secondary Aim: What is the preliminary comparative efficacy of W-GenZD and CBT-lite telehealth zoom groups to manage mood and anxiety concerns?

Hypothesis: W-GenZD will be non-inferior to CBT-lite with regards to the secondary endpoints at 4-weeks end-of-treatment

Secondary Endpoints:

• PHQ-8

Analysis Plan:

To assess the secondary aim non-inferiority tests will be used. The secondary analysis will focus on meeting the secondary aim of an initial test of the non-inferiority of W-GenZD as compared to CBT-lite telehealth zoom, to manage mood concerns. An intent-to-treat analysis will be used with participants analyzed as assigned to the treatment conditions. Mean, standard deviation, median, first quartile, third quartile, minimum, maximum and interquartile range (IQR) will be reported for each variable at each time point. A non-inferior test will be employed. The margin of clinical significance for the outcomes will be set to 2. These tests will be performed for each variable using the end of treatment time point. In addition, a meta-analysis will be performed to assess the active control effect of the cbt-based telehealth in a pediatric population. Full details will be specified in the SAP.

Tertiary Aim: Investigate potential between group differences..

Tertiary Endpoints:

- Working Alliance Inventory-SR (WAI-SR)
- GAD-7
- MFQ

Analysis Plan:

The tertiary analysis will focus on meeting the tertiary aim of an initial test of the potential between group differences on the WAI-SR, GAD-7, and MFQ. An intent-to-treat analysis will be used with participants analyzed as assigned to treatment conditions.

Woebot Health W-GenZD-003

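### Does the PHQ-8 non-inferiority test need an exposure-based analysis beside intent-to-treat?

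*Combined protocol and SAP*

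**What the plan says.** Section 9 (Statistical Analysis, Secondary Aim) hypothesises that W-GenZD is non-inferior to CBT-lite on PHQ-8 at Week 4, sets the margin at 2, calls this an initial test, and states: "An intent-to-treat analysis will be used with participants analyzed as assigned to the treatment conditions". It leaves full details to the SAP; the supplied file contains no separate SAP text.

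Section 3.3.1 defines who is in that analysis. Participants who do not register for the app or attend a group in the first week stay in the study and may start late. Everyone randomized, "regardless of participation or withdrawal status, will be included in the intent-to-treat analysis".

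The opening of Section 9 says the study was "designed to assess the feasibility of delivering W-GenZD as an option" for adolescents on a waiting list.

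Exposure is recorded in both arms. App measures include "number of messages sent to Woebot by week and number of days active in the app by week", and "For subjects in the Woebot condition the app engagement measures will be summarized". Section 5.6 has group attendance recorded through Week 4, and Section 2 lists it as a feasibility metric. The exploratory aim in Section 2 will "examine associations between these factors and study clinical, alliance, engagement and satisfaction outcomes", but those factors are healthcare utilization, social determinants and comorbidity. Engagement is an outcome there, not a predictor of PHQ-8.

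**The concern.** In a superiority trial, non-use usually works against the new treatment. In a non-inferiority trial it can work in its favour: participants who take up neither intervention tend to have similar outcomes, so a real deficit among users shrinks towards zero. A second analysis restricted to, or adjusted for, adequate exposure is therefore often expected beside intent-to-treat.

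The protocol gives some cause for worry. Section 3.3.1 foresees participants who do not start, and Section 1.3 reports for internet interventions "a median minimal completion rate (usually defined as completion of ~4 sessions) of 56" percent. The secondary aim speaks of preliminary comparative efficacy. A reader could fear that a result inside the margin reflects low exposure rather than similar effects. If non-use is concentrated in the app arm, a result outside the margin might reflect poor uptake rather than a weaker app.

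**Working it through.** **Inputs.** From the protocol: margin 2 (Section 9) and about 130 per arm (Section 3.1). Alpha, SD, dropout and expected non-use are not stated, and 260 is given without the inputs needed to reproduce it. Assumed: one-sided 2.5%; SD 5, range 4.2 to 6 (4.2 is the SD of the 2-week PHQ-9 change in Woebot participants aged 18-21, Section 1.2.1); complete Week 4 data; no effect in non-users; a deficit among users of exactly 2.

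**Step 1: dilution.** With a share p of non-users in each arm, the true intent-to-treat difference is 2(1 - p). The standard error is 5 × sqrt(2/130) = 0.620. The chance of declaring non-inferiority is Φ((2 - difference)/0.620 - 1.96).

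| p | True difference | Declared, SD 5 | SD 6 to SD 4.2 |
|---|---|---|---|
| 0% | 2.00 | 2.5% | 2.5% |
| 10% | 1.80 | 5.1% | 4.5% to 5.8% |
| 20% | 1.60 | 9.4% | 7.7% to 11.7% |
| 30% | 1.40 | 16.0% | 12.4% to 21.0% |
| 44% | 1.12 | 29.4% | 21.8% to 39.3% |

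The last row treats the complement of the 56% in Section 1.3 as non-use with no effect. Non-completion is not non-use: if these participants keep half the effect, the difference is 2(1 - 0.22) = 1.56 and the figure falls to 10.6%.

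**Step 2: are these errors?** The null hypothesis is a difference of 2 or more. For every p above zero, the true difference between the arms as randomized is below 2. The declarations are therefore correct for the effect of offering one programme rather than the other. They are wrong only for the effect among users. Section 3.3.1 keeps non-starters on purpose, and Section 9 frames W-GenZD as an option to be delivered, so the as-offered effect is the one asked about.

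**Step 3: the other direction.** Assume a CBT-lite effect of 3 among attenders, with 10% non-use in CBT-lite and 44% in the app arm. With a user deficit of 2, the difference is 3 × 0.90 - 1 × 0.56 = 2.14, declared non-inferior in 1.4% of trials. With users doing equally well, it is 3 × (0.90 - 0.56) = 1.02, and power falls from 89.7% to 35.2%. Again the test responds correctly to what was delivered, and uptake by arm can be seen from data already collected.

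**Step 4: what would an analysis among users add?** Let a share q = 1 - p qualify in each arm. The chance SD of the shift between the two estimates is sqrt(SE_users² - SE_ITT²). The expected shift for a user deficit of 2 is 2p.

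| q | SE among users | SD of shift | 95% band | Expected shift | Exceeds band |
|---|---|---|---|---|---|
| 80% | 0.693 | 0.310 | ±0.61 | 0.40 | 25% |
| 70% | 0.741 | 0.406 | ±0.80 | 0.60 | 31% |
| 56% | 0.829 | 0.550 | ±1.08 | 0.88 | 36% |

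With no true difference, power among users is 82.2%, 77.0% and 67.5%. By chance alone, the smaller set misses the margin after an intent-to-treat success in 9.8%, 15.7% and 26.2% of cases.

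**Step 5: selection.** Now assume no treatment difference at all. CBT-lite attenders have a prognosis 2 points better than non-attenders, and app users are unselected. Dropping the non-attenders lowers the CBT-lite mean by 2p and leaves the app mean unchanged, so the estimate again shifts by 2p: 0.40, 0.60 and 0.88. A simulation of 20,000 trials per setting (SD 5, 130 per arm) gave mean shifts of 0.40, 0.59 and 0.88, exceeding the band in 26%, 31% and 36% of trials. This pattern is practically indistinguishable from that of a true 2-point deficit among users.

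**The case for a change.** The strongest case for acting is that an exposure-based analysis is cheap and that its main value lies in timing. Exposure data exist in both arms, and a threshold fixed before outcomes are seen cannot be tuned afterwards. Summaries of uptake show that exposure was low but not what it did to PHQ-8. It is also true that no supplied section describes a per-protocol, as-treated, compliance-adjusted or dose-response analysis of PHQ-8, and that the exploratory associations do not fill that place.

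Those facts stand, and so does the arithmetic of dilution. They do not make a defect. The analysis could not serve as a second success criterion, because chance misses are frequent (Step 4). Read only as a shift in the estimate, it cannot tell a weaker app from self-selection (Step 5). Exposure thresholds for app days and group sessions have no common scale, yet the resulting subsets would be held against the same margin of 2. Supporting analysis sets are also ordinary SAP content, and Section 9 leaves full detail of this very analysis to the SAP, so their absence from the protocol does not show that none is planned.

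The high non-use scenario is not well grounded for this product either. Section 1.2.1 reports a mean of 12.14 engagements in 2 weeks, range 8-18. That comes from an early prototype in 18-28 year olds, so it does not settle uptake in this trial.

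**Conclusion.** The concern does not hold. Intent-to-treat matches the as-offered question set by Sections 3.3.1 and 9. Followed as written, the plan gives a sound answer to it. The 5.1% to 29.4% declaration rates (SD 5, 10% to 44% equal non-use, no effect in non-users) are not error rates of the planned test, because the true difference between the arms is then 1.8 to 1.12, below the margin of 2.

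They would be errors only for an effect among users, which the protocol does not set out to test. A supporting analysis aimed at that effect would detect a 2-point user deficit in only 25% to 36% of trials at 20% to 44% non-use, and selection could imitate it. For a secondary, initial test in a feasibility trial, statisticians may reasonably differ on whether to add one; leaving it out changes no result.

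All sizes rest on the assumed alpha, SD, complete data and non-use. The conclusion about which question intent-to-treat answers does not depend on them.

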Key Results: In the broader cohort of all participants ages 18-28 years, those in the Woebot group significantly (F=6.5; p=.01) reduced their symptoms of depression over the study period as measured by the Patient Health Questionnaire (PHQ-9), relative to those in the control group [26]. Participants engaged with the device an average of 12.14 times (SD=2.23; median=12; range 8-18) over the 2-week study period. As it relates specifically to the subgroup of interest, 37% of participants (n=26/70) were ages 18-21 years. Intent-to-treat analysis indicated that Woebot participants ages 18-21 years experienced a reduction in symptoms of depression as measured by the PHQ-9 (mean reduction = 1.7, SD (4.2)), and in symptoms of anxiety as measured by the Generalized Anxiety Disorder (GAD-7) scale (mean reduction = 1.7, SD (3.2)) at 2-weeks, as compared to baseline. Within-subject effect sizes on both measures were small to medium (Cohen's d = .27 and .31 for PHQ-9 and GAD-7, respectively); neither of these differences was statistically significant (t = -1.9, p = .09 and t = -1.4, p = 0.19, respectively) at 2-weeks, relative to baseline, due the limited sample size as the original study was powered for the full 18-28 range. However, the subgroup results show a trend that is consistent with the overall results.

Conclusion: RCT results indicated that W-GenZD was a feasible, effective, and engaging way to digitally deliver CBT to participants self-identifying as having symptoms of depression or anxiety, in the adolescent population ages 18-28. Results in the 18-21 subgroup were consistent with those in the larger study, but were not statistically significant since the study was originally powered for the larger group.

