4.1.2 CBT-Lite Teletherapy Groups

The CBT-Light teletherapy groups aim to provide support to adolescents seeking treatment after they have been triaged into CHKD's low-intensity track. In the clinical setting, CHKD offers CBT-lite teletherapy groups for youth with low intensity symptoms who are waiting for individual care, as described above. The research-specific groups are a brief, 4-week intervention held once weekly for an hour, and limited to those participating in this protocol. Enrolled participants randomized to group are offered the group that best fits their schedule. An assigned study clinician will facilitate each teletherapy group with up to 10 adolescents in each session. Each group begins with orientation and reviewing group rules, individual check-ins with each participant (rating stress level and hopefulness), followed by a guided mindfulness moment.

Groups will be conducted on an open-enrollment, rolling topic basis, allowing for participants to join the next available session following randomization and complete all 4 sessions during their study treatment period. Sessions are designed to draw from elements of CBT and the 4 topics include: Building a coping tool box, Accept your feelings, Challenge negative thoughts, and Problem solving. Fidelity to group process is monitored by non-clinician study team member.

Participants randomized to the CBT-Lite TeletherapyGroup will be offered access to the Woebot LIFE app at the end of study.

5. Study Assessments and Procedures

All assessments, and their corresponding administration points, are listed in Table 1.

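### The PHQ-8 non-inferiority test rests on intent-to-treat alone, with no supportive between-arm analysis that accounts for non-use of the assigned treatment

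*Combined protocol and SAP*

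**What the plan says.** The Secondary Aim in Section 9 concerns preliminary comparative efficacy, and its hypothesis is that W-GenZD is non-inferior to CBT-lite at the end of treatment. The margin reads: "The margin of clinical significance for the outcomes will be set to 2". No unit is given; since the PHQ-8 is the only endpoint listed under that aim, I read it as PHQ-8 points.

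On the population, Section 9 says: "An intent-to-treat analysis will be used with participants analyzed as assigned to the treatment conditions". Section 3.3.1 states that participants who do not register for the app or attend a group in the first week stay in the study, and adds: "All participants randomized to this protocol, regardless of participation or withdrawal status, will be included in the intent-to-treat analysis".

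Use is measured in both arms. Section 5.6 collects days in the app and group attendance, and Section 9 lists active days by week. The plan summarises the engagement measures and lists attendance as a feasibility metric. The exploratory aim in Section 2 relates healthcare utilization, social determinants and comorbidity to outcomes that include engagement. None of these compares PHQ-8 between arms while accounting for use.

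Section 9 also plans a meta-analysis of the control effect: "In addition, a meta-analysis will be performed to assess the active control effect of the cbt-based telehealth in a pediatric population". It gives no timing and does not say how the result bears on the conclusion. The next sentence is "Full details will be specified in the SAP". No separate SAP text is among the documents supplied.

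**The concern.** In a superiority trial, non-use usually works against the sponsor. In a non-inferiority trial it can work the other way: if participants in both arms leave their treatment unused and then fare alike, the arms look more similar than the treatments are. When the app is truly worse among those who use it, the ITT difference moves toward zero and a pass becomes easier.

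Section 1.3 itself reports poor adoption and adherence for internet interventions, so non-use is foreseeable. If it is common in both arms, a reader of an ITT pass cannot tell whether the two treatments perform alike or whether too few people took them up to show a difference. Nothing planned would help separate these explanations.

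A smaller matter is the undated meta-analysis. With no untreated arm, its result affects how far a pass can be read, so it should not be left open until by-arm results are known.

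**Working it through.** **The plan's own figure.** Section 3.1 gives a minimum of 260 participants, about 130 per arm, without a calculation. No alpha, power, SD or dropout is stated, so 260 can be neither reproduced nor refuted. With SD 5, one-sided 2.5%, 90% power and no true difference, n per arm = 2 × 5² × (1.960 + 1.282)² / 2² = 131.4, so 132 per arm or 264 in total. That is close to 260, but it is a back-fit and not evidence of the sponsor's inputs.

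**Inputs**
- Margin 2: Section 9.
- n = 130 per arm: Section 3.1.
- One-sided alpha 2.5%: assumed.
- SD 5, range 4.2 to 6.3: assumed. The only PHQ spread in the documents is in Section 1.2.1 (PHQ-9, ages 18 to 21, early prototype, 2 weeks): SD 4.2 beside a mean reduction of 1.7. If the reported effect size of .27 is that reduction over a score SD, then SD = 1.7/0.27 = 6.3. The figures do not agree with each other, since 1.7/4.2 = 0.40, so the range is only a working assumption.
- Non-use share u, equal in both arms, with non-users gaining nothing: assumed.

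**Dilution.** For a true deficit of 2 points among users:

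ITT deficit d = 2 × (1 − u)

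SE = SD × √(2/130), which is 0.521, 0.620 and 0.781 for SD 4.2, 5 and 6.3

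P(pass) = Φ((2 − d)/SE − 1.96)

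| Non-use, both arms | ITT deficit d | SD 4.2 | SD 5 | SD 6.3 |
|---|---|---|---|---|
| 0% | 2.0 | 0.025 | 0.025 | 0.025 |
| 20% | 1.6 | 0.117 | 0.094 | 0.074 |
| 40% | 1.2 | 0.336 | 0.251 | 0.175 |

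Worked case, SD 5 and 20% non-use: (2 − 1.6)/0.620 = 0.645; 0.645 − 1.960 = −1.315; Φ(−1.315) = 0.094.

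Section 1.3 cites a median minimal completion of 56%. It describes completing about four sessions, not access to treatment, so I do not use 44% as a non-use rate.

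**Unequal non-use.** Let CBT-lite users gain C, app users gain C − 2 and non-users gain nothing. Then d = C × (1 − u_control) − (C − 2) × (1 − u_app). With C = 4, purely as an assumption:
- 20% non-use of the app, 40% of the groups: d = 2.4 − 1.6 = 0.8, so a pass is easier.
- 40% non-use of the app, none of the groups: d = 4.0 − 1.2 = 2.8, so a pass is harder than with full use.

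The direction is therefore not fixed in advance.

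**Precision of a users-only analysis.** With no true difference, power = Φ(2/SE − 1.96). At SD 5, with equal exposure in both arms and before missing outcomes:
- 100% exposed (130 per arm): 0.897.
- 80% exposed (104 per arm): SE 0.693, power 0.822.
- 60% exposed (78 per arm): SE 0.801, power 0.705.

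**The case against.** **ITT answers a legitimate question.** Section 9 presents the study as one of delivering the app as an option to adolescents on a waiting list, and ITT estimates the effect of that offer. With 20% non-use, a 2-point deficit among users is a 1.6-point deficit under the offer. That lies inside the margin, so a pass is correct for that question. This stands. A reader might infer from the table that the planned test has an inflated error rate; it does not. The table shows how an ITT pass can coexist with a 2-point deficit among users.

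**Dilution is conditional.** It favours a pass only if the app is worse among users and non-users fare alike. This also stands, as the unequal cases show. It limits the claim to what can happen.

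**Non-use will be visible.** Engagement and attendance will be described. That helps, but a description of uptake does not estimate the between-arm difference among users.

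**The SAP may cover it.** Section 9 defers details there, so the finding is absence from the supplied documents, not from the whole plan.

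**The stronger reading of the meta-analysis gap.** A reader might infer that the margin is too wide, or that the sponsor will present a pass as benefit over no treatment. The documents support neither. They give no control effect against which to judge 2, and the hypothesis is only relative to CBT-lite. The remark in Section 8.2 about data on the efficacy of Woebot is a general benefit statement outside the analysis plan. Planning to estimate the control effect shows that the sponsor anticipated the issue; what is missing is detail.

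**Conclusion.** The point holds as a minor one. The non-inferiority test has ITT as its only named population, never-users are included, and the supplied documents plan no between-arm PHQ-8 analysis that accounts for use. For a comparative-efficacy aim, that leaves an ITT pass harder to interpret if non-use is substantial in both arms.

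At SD 5, the chance that a true 2-point deficit among users passes rises from 2.5% to 9% at 20% non-use and 25% at 40%. These figures rest on an assumed SD, alpha, equal non-use and no gain in non-users; actual non-use is unknown. They are not a flaw in the ITT test itself. The aim is secondary and described as preliminary, and the descriptive primary aim is unaffected.

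The undated meta-analysis is a clarification only. The planned test already delivers the statement that the app is not worse than CBT-lite by more than 2 points.

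**What to change.** Keep the ITT test at a margin of 2 as the decisive analysis. Add to Section 9 one supportive between-arm PHQ-8 analysis at week 4 among participants who used their assigned treatment:
- Define use from the days-active and group-attendance data already collected, with a threshold fixed before anyone sees outcomes by arm. At least one active app day or one group attended is a possible example. It is my choice, not the protocol's, and it is weak evidence of treatment received.
- Report the estimate with its 95% CI and say whether it agrees with ITT.

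As a secondary clarification, state in the SAP that the control-effect meta-analysis is completed before by-arm outcomes are seen. State also that a pass means not worse than CBT-lite by more than 2 points, unless that meta-analysis supports a control effect above 2. If a separate SAP already says this, a cross-reference is enough.

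The cost is wording, a date for work already planned and one further analysis, with no extra participants or procedures. The downside is that the users-only set is not protected by randomisation. It is also less precise: at SD 5, power falls from about 90% to about 82% at 80% exposure and about 70% at 60%, and further with missing outcomes. It should therefore support ITT and never override it.
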